**5.5.7 Pharmacokinetics**

Pharmacokinetics will be tabulated for each collection day using descriptive statistics. Mean plasma concentrations will be plotted through time using both linear and semi-logarithmic scales. Plasma concentrations will also be plotted through time for each subject, using both linear and semi-logarithmic scales. Concentrations below the limit of quantitation will be set to zero for descriptive statistics.

The following PK parameters will be calculated for Day 15 (steady state trough level only) and Day 29 [steady state ( $\pm$ specified window)]:

- $C_{\max}$ : maximum observed plasma concentration
- $T_{\max}$ : time to maximum observed plasma concentration
- $AUC_{0-24}$ : area under the plasma concentration-time curve from Hour 0 to Hour 24, calculated using the linear trapezoidal rule
- $AUC_{0-\infty}$ : area under the plasma concentration-time curve extrapolated to infinity
- $\lambda_Z$ : elimination rate constant
- $t_{1/2}$ : elimination half-life

PK parameters will be calculated using actual sampling times.

### **5.5.8 Safety Analyses**

No imputation will be made for missing safety data.

#### **5.5.8.1 Extent of Exposure**

The extent of exposure to study drug will be summarized by the total number of days of dosing, total number of applications, and total amount of study drug applied.

#### **5.5.8.2 Adverse Events**

All AEs occurring during the study will be recorded and classified on the basis of *Medical Dictionary for Regulatory Activities* terminology. TEAEs are those with an onset on or after the time of the first study drug administration. For the safety population, all reported TEAEs will be summarized by system organ class (SOC), preferred term, severity, relationship to study drug, and seriousness. When summarizing TEAEs by causality and severity, each subject will be counted only once within an SOC or a preferred term using the event with the closest relationship to study drug and the greatest severity within each classification.

SAEs will be summarized by severity and relationship to study drug, and individual SAEs will be listed by subject. A list of subjects who prematurely discontinued from the study due to an AE will also be provided.

All information pertaining to AEs noted during the study will be listed by subject, detailing the verbatim term reported by the Investigator, preferred term, SOC, onset date, resolution date, maximum severity, seriousness, action taken regarding study drug, corrective treatment, outcome, and drug relationship. The event onset will also be shown relative (in number of days) to date of first administration of study drug.

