#### **5.4.3.4 Adverse Events**

An AE is any untoward medical occurrence or unintended change from the subject's Baseline (pretreatment) condition, including intercurrent illness, that occurs during a clinical trial after treatment has started, whether or not it is considered related to study treatment. An AE can therefore be any unfavorable and unintended sign (including an abnormal laboratory finding), symptom, or disease temporally associated with the use of an investigational product.

An AE is meant to include events that are either new or represent detectable exacerbations of preexisting conditions, and does not imply any judgment about causality.

AEs will be assessed at each visit. Any AE occurring on or after the date of the dose of study drug administration on Day 1 and up to and including the completion/termination date will be counted as treatment-emergent.

Adverse experiences may include but are not limited to subjective or objective symptoms spontaneously reported by the subject and/or observed by the Investigator or medical staff, including laboratory abnormalities of clinical significance. Preexisting conditions noted as part of the medical history at Screening must be reported on the appropriate medical history CRF page. Stable, ongoing conditions present at Screening should not be recorded as AEs if the severity at Screening remains unchanged during the study. However, preexisting conditions for which an increase in severity is observed after Screening must be recorded as AEs.

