**KERYDIN® (N=xx)**

	Baseline	Week 2	Week 4	Week 8	Week 16	Week 24
Scaling						
N	xx	xx	xx	xx	xx	xx
Mean	x.x	x.x	x.x	x.x	x.x	x.x
SD	x.xx	x.xx	x.xx	x.xx	x.xx	x.xx
Median	xx.x	xx.x	xx.x	xx.x	xx.x	xx.x
Min. to Max.	x to x	x to x	x to x	x to x	x to x	x to x
Change from Baseline						
N		xx	xx	xx	xx	xx
Mean		x.x	x.x	x.x	x.x	x.x
SD		x.xx	x.xx	x.xx	x.xx	x.xx
Median		xx.x	xx.x	xx.x	xx.x	xx.x
Min. to Max.		x to x				
Scaling		Week 32	Week 40	Week 48	Week 52	
N		xx	xx	xx	xx	
Mean		x.x	x.x	x.x	x.x	
SD		x.xx	x.xx	x.xx	x.xx	
Median		xx.x	xx.x	xx.x	xx.x	
Min. to Max.		x to x	x to x	x to x	x to x	
Change from Baseline						
N		xx	xx	xx	xx	
Mean		x.x	x.x	x.x	x.x	
SD		x.xx	x.xx	x.xx	x.xx	
Median		xx.x	xx.x	xx.x	xx.x	
Min. to Max.		x to x	x to x	x to x	x to x	

Note: No imputation of missing data.

Listing 16.2.7.1

SOURCE: USERNAME\SPONSOR\PROJECT\JOBNAME (DATE,TIME)

Table 14.3.1.2.1: Summary of Treatment-Emergent Adverse Event Characteristics  
 (Safety Population)  
 (Page 1 of 2)

	KERYDIN® (N=xx)
Subjects Reporting Any Adverse Event	xx ( xx.x%)
Subjects Reporting Any Serious Adverse Event	xx ( xx.x%)
Subjects Who Died	xx ( xx.x%)
Subjects Who Discontinued Study Drug Due to Adverse Event	xx ( xx.x%)
Total Number of Adverse Events Reported	xx
By Subject	
By Maximum Severity	
Mild	xx ( xx.x%)
Moderate	xx ( xx.x%)
Severe	xx ( xx.x%)
By Strongest Relationship to Study Drug	
Definite	xx ( xx.x%)
Probable	xx ( xx.x%)
Possible	xx ( xx.x%)
Unlikely	xx ( xx.x%)
Not Related	xx ( xx.x%)

Note: Treatment-emergent adverse events are those with an onset on or after the first application of study drug.

Listing 16.2.7.2.3

SOURCE: USERNAME\SPONSOR\PROJECT\JOBNAME (DATE,TIME)

Table 14.3.1.2.1: Summary of Treatment-Emergent Adverse Event Characteristics  
 (Safety Population)  
 (Page 2 of 2)

		KERYDIN® (N=xx)
By Subject		
Maximum Severity within Relationship to Study Drug		
Definite		
Mild		xx ( xx.x%)
Moderate		xx ( xx.x%)
Severe		xx ( xx.x%)
Probable		
Mild		xx ( xx.x%)
Moderate		xx ( xx.x%)
Severe		xx ( xx.x%)
Possible		
Mild		xx ( xx.x%)
Moderate		xx ( xx.x%)
Severe		xx ( xx.x%)
Unlikely		
Mild		xx ( xx.x%)
Moderate		xx ( xx.x%)
Severe		xx ( xx.x%)
Not Related		
Mild		xx ( xx.x%)
Moderate		xx ( xx.x%)
Severe		xx ( xx.x%)

Note: Treatment-emergent adverse events are those with an onset on or after the first application of study drug.

Listing 16.2.7.2.3

SOURCE: USERNAME\SPONSOR\PROJECT\JOBNAME (DATE,TIME)

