## 7. INDEX OF PLANNED LISTINGS

Listing 16.2.1.1: End of Study Information .....
Listing 16.2.1.2.1: Discontinued Subjects .....
Listing 16.2.2: Inclusion/Exclusion Criteria Violations .....
Listing 16.2.3: Analysis Populations .....
Listing 16.2.4.1: Subject Demographic Information .....
Listing 16.2.4.2: Medical History .....
Listing 16.2.4.3.1: Unique Medication Names Coded to WHO-DD ATC Level 2 Terms and Preferred Names .....
Listing 16.2.4.3.2: Prior and Concomitant Medications .....
Listing 16.2.4.4: Prior and Concomitant Therapies and Procedures .....
Listing 16.2.5.1: Study Visit Compliance .....
Listing 16.2.5.2: Study Medication Accountability Log .....
Listing 16.2.5.3: Dosing Diary Information .....
Listing 16.2.6.1: Target Great Toenail Assessments .....
Listing 16.2.6.2: Non-Target Great Toenail Assessments .....
Listing 16.2.6.3: Pharmacokinetic Blood Draw Information .....
Listing 16.2.6.4: Pharmacokinetic Parameters .....
Listing 16.2.7.1: Local Tolerability Reactions .....
Listing 16.2.7.2.1: Unique Adverse Events Coded to MedDRA System Organ Classes and Preferred Terms .....
Listing 16.2.7.2.2: Pre-Treatment Adverse Events .....
Listing 16.2.7.2.3: Treatment-Emergent Adverse Events .....
Listing 16.2.7.2.4: Serious Adverse Events .....
Listing 16.2.7.2.5: Subjects Who Permanently Discontinued Study Drug and/or Discontinued from the Study Due to Adverse Events .....
Listing 16.2.8.1: Pregnancy Tests .....
Listing 16.2.8.2.1: Laboratory Results .....
Listing 16.2.8.2.2: Abnormal Laboratory Results .....
Listing 16.2.8.3: Vital Signs .....

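### The TEAE rule is based on onset only and does not cover an adverse event that starts between Screening and Day 1 and worsens after dosing

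*SAP*

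**What the plan says.** The SAP gives the treatment-emergent rule in three places.

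- Section 5.5.8.2: "TEAEs are those with an onset on or after the time of the first study drug administration".
- Footnote to Table 14.3.1.2.1 and the TEAE tables after it: "Treatment-emergent adverse events are those with an onset on or after the first application of study drug". The serious-event tables (14.3.2.2.1 to 14.3.2.2.4) carry the same rule for serious events.
- Section 5.4.3.4: "Any AE occurring on or after the date of the dose of study drug administration on Day 1", with the window running "up to and including the completion/termination date will be counted as treatment-emergent".

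Section 5.4.3.4 also defines what an AE is. It includes an "unintended change from the subject's Baseline (pretreatment) condition" and states that detectable exacerbations of pre-existing conditions count. For those conditions it then changes the reference point to Screening: "Stable, ongoing conditions present at Screening should not be recorded as AEs if the severity at Screening remains unchanged during the study", but "preexisting conditions for which an increase in severity is observed after Screening must be recorded as AEs".

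The schedule in 5.1.1 has AEs collected from Screening, up to 70 days before Day 1. Section 7 plans a separate "Listing 16.2.7.2.2: Pre-Treatment Adverse Events". Section 5.5.8.2 lists one onset date, one resolution date and a maximum severity for each AE, and no date on which severity changed.

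**The concern.** Safety and tolerability are the primary objective (section 4), and every AE summary table in the section 6 index is restricted to treatment-emergent events. An event that starts in the screening interval and becomes worse under study drug is one that a safety reader would want counted. A rule that looks only at onset sends it to the pre-treatment listing. It would then be absent from the tables by system organ class and preferred term, severity, relationship, and withdrawal.

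The omission runs in one direction. Leaving such an event out cannot raise an overall or preferred-term count. In the severity tables, where a subject is counted once at the greatest severity, it can also move a subject with a second, milder event in the same class to a lower grade.

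**Working it through.** The plan states no figure on this point, so there is none to reproduce. The check traces each type of event through the text.

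**1. New event after the first application.** Onset is after dosing. It is a TEAE under all three wordings.

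**2. Medical-history condition, stable through Day 1, that worsens on treatment.** Section 5.4.3.4 requires it to be recorded as an AE. If onset is dated at the worsening, it is a TEAE and stays in the tables. The SAP does not state that dating rule, but the AE record is first opened after dosing, so this is the natural reading. Clinically significant Baseline laboratory abnormalities follow the same route, because section 5.4.3.3 sends them to medical history.

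**3. AE that begins between Screening and Day 1 and worsens after dosing.** As an illustration, take an event that starts as mild on Day -20 and becomes severe at Week 8.

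- It is recorded before dosing: the schedule collects AEs from Screening, and section 7 has a listing for such events.
- Its onset date is before Day 1, so it fails the test in 5.5.8.2 and in the footnotes.
- Its maximum severity field can be updated to severe, but the onset date does not move.
- No text opens a new record at the worsening or re-dates the event.
- Followed as written, it stays in the pre-treatment listing and enters no TEAE table.

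Under the 5.4.3.4 wording, the same event could be said to be *occurring* after the Day 1 dose and so be treatment-emergent. The two sections can thus classify it differently, and the footnotes that go onto the tables follow the onset wording.

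**Scale.** The only fixed number is the minimum of 40 subjects aged 12 to 16 years and 11 months (section 5.5.9). Total enrolment is not fixed.

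- Effect per affected subject on a TEAE percentage = 1/N.
- With N = 40: 1/40 = 2.5 percentage points. With any larger N it is smaller.
- On the any-TEAE row the effect is zero for a subject who has another TEAE.

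The number of affected subjects cannot be obtained from the plan, so no total follows.

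**The case against.** The best defence is that 5.4.3.4 describes an AE as something that happens after treatment has started and includes exacerbations. On that reading an on-treatment worsening is an AE in its own right, with its own on-treatment onset, and is a TEAE even under the onset rule. How worsening is recorded and dated may also be set in the protocol or CRF guidelines, which are not shown. This reading is possible, but nothing in the SAP establishes it, and the same document plans a listing of AEs from before treatment. A rule that decides which events enter the primary safety tables should not depend on it.

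A second objection stands and limits the consequence. Section 5.5.8.2 lists all AEs noted during the study. The listings of pre-treatment events, serious events and discontinuations due to AEs are not titled as TEAE-only. Table 14.1.1.1 counts discontinuation for an adverse event with no TEAE restriction. Local tolerability, laboratory values and vital signs are summarised as change from Baseline (5.5.8.3 to 5.5.8.5), so worsening in those measures is unaffected.

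Two stronger readings are tempting but not supported.

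- A reader might infer that a condition which improves by Day 1 and then relapses to its Screening severity is excluded from recording. The exemption covers only stable, ongoing conditions whose severity is unchanged during the study. A condition that improves and relapses does not plainly fit, and its relapse can be read as an increase observed after Screening, which must be recorded.
- A reader might make much of *date* in 5.4.3.4 against *time* in 5.5.8.2, or of the end of window given only in 5.4.3.4. The first matters only for events on Day 1 before application. The second has almost no effect, because AE collection in the schedule ends at Visit 11 or early termination.

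**Conclusion.** The point holds for one class of event: AEs that begin between Screening and Day 1 and worsen after dosing. Under 5.5.8.2 and the table footnotes as written, these can be left out of all TEAE summary tables although 5.4.3.4 treats exacerbations as AEs. The conclusion assumes that such an event stays on one record with its original onset date. The listed fields are compatible with this, but the SAP neither requires nor rules it out.

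Any bias is toward a lower TEAE rate. It is at most 2.5 percentage points per affected subject, provided the safety population is at least 40. Multiplying that by a guessed number of events would give a total that the documents do not support. The study is single-arm and descriptive and the events remain in the listings, so this is a correctable gap in the summary of the primary objective. It does not undermine the study.

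**What to change.** Use one definition, in the same words, in 5.4.3.4, 5.5.8.2 and the footnotes to the TEAE and serious-TEAE tables:

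*A treatment-emergent AE is an AE with onset, or with an increase in severity over the last pre-dose state, on or after the first application of study drug and no later than the subject's completion or termination date. For a pre-dose event that worsens, the date of worsening is used as the onset.*

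Reconcile the two reference points in 5.4.3.4, so that the AE definition (Baseline) and the recording rule for pre-existing conditions (Screening) refer to the same state. The last pre-dose state is the natural choice: 5.5.8.4 already uses the last pre-dose value for laboratory data, and the schedule already reviews medical history at Visit 2.

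The cost is SAP wording and minor programming, including capture of the worsening date if it is not already held. No new visits or assessments are needed. The reported TEAE rate may be slightly higher.

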### **5.5.8.3 Local Skin Reactions**

LTRs (burning/stinging, induration/edema, oozing and crusting, pruritus, erythema, and scaling) will be evaluated by frequency tables for Baseline and Weeks 2, 4, 8, 16, 24, 32, 40, 48, and 52. Additionally, LTRs as well as change from baseline in LTRs will be summarized by descriptive statistics (mean, standard deviation, median, and minimum and maximum).

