### 4. STUDY OBJECTIVES

The primary objective of this study is to assess the safety and tolerability of KERYDIN (tavaborole) topical solution, 5% applied once daily for 48 weeks in pediatric subjects ages 6 to 16 years and 11 months with onychomycosis of the toenails.

The secondary objective is to perform PK assessments in a subgroup of at least 16 evaluable subjects ages 12 to 16 years and 11 months following topical administration under maximal use conditions.

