## **5.4.3 Safety Variables**

### **5.4.3.1 Local Tolerability Reactions**

Safety evaluations will include local tolerability reactions (LTRs) (burning/stinging, induration/edema, oozing and crusting, pruritus, erythema, and scaling), as reported by the subject and/or evaluated by the Investigator at Baseline and each study visit thereafter. LTRs will be documented on the case report form (CRF) specifically designed to capture LTR information (local tolerability signs CRF) and not on the AE CRF. LTRs that require treatment (eg, with a concomitant medication or drug interruption or drug discontinuation) are an exception to this guideline; these LTRs should be documented on both the local tolerability signs CRF and on the AE CRF.

Grade	Guideline
Burning/Stinging	
0 - None	No stinging/burning
1 - Mild	Slight warm, tingling sensation; not really bothersome
2 - Moderate	Definite warm; tingling/stinging sensation that is somewhat bothersome
3 - Severe	Hot, tingling/stinging sensation that has caused definite discomfort
Induration/Edema	
0 - None	No elevation
1 - Mild	Barely perceptible elevation
2 - Moderate	Clearly perceptible elevation but not extensive
3 - Severe	Marked and extensive elevation
Oozing and Crusting	
0 - None	Absent
1 - Mild	Faint signs of oozing
2 - Moderate	Definite oozing or crust but with 5 or fewer sites per area
3 - Severe	Marked and extensive oozing and crusting
Pruritus	
0 - None	No pruritus
1 - Mild	Occasional, slight itching/scratching
2 - Moderate	Constant or intermittent itching/scratching which is not disturbing sleep
3 - Severe	Severe bothersome itching/scratching which is disturbing sleep
Erythema	
0 - None	No redness present
1 - Mild	Faintly detectable erythema; very light pink
2 - Moderate	Dull red, clearly distinguishable
3 - Severe	Deep/dark red
Scaling	
0 - None	No scaling
1 - Mild	Barely perceptible shedding, noticeable only on light scratching or rubbing
2 - Moderate	Obvious but not profuse scaling
3 - Severe	Heavy scale production

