### **5.5.8.4 Safety Laboratory Values**

Laboratory values as well as changes from Baseline in laboratory values will be summarized with descriptive statistics at Baseline, Week 24 and Week 52. In addition, shift tables will be created according to normal ranges. The last laboratory evaluation before the first dose of study drug will be used as Baseline for all laboratory analyses.

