## 6. INDEX OF PLANNED END-OF-TEXT TABLES

Table 14.1.1.1: Summary of Subject Completion/Discontinuation.....	23
Table 14.1.1.1.1: Summary of Subject Enrollment and Evaluability .....	24
Table 14.1.2.1: Summary of Subject Demographic Characteristics (Safety Population).....	25
Table 14.1.2.2: Summary of Subject Demographic Characteristics (PK Population).....	26
Table 14.1.2.3: Summary of Subject Baseline Characteristics (Safety Population).....	27
Table 14.1.2.4: Summary of Subject Baseline Characteristics (PK Population).....	28
Table 14.2.1: Summary of Clinical and Mycological Characteristics by Visit (Safety Population).....	29
Table 14.2.2: Summary of the Primary Efficacy Endpoint: Complete Cure at Week 52 (Safety Population).....	30
Table 14.2.3: Summary of Secondary Efficacy Endpoints (Safety Population).....	31
Table 14.3.1.1.1: Summary of Local Tolerability Reactions by Visit (Safety Population).....	33
Table 14.3.1.1.2: Means Summary of Local Tolerability Reactions by Visit (Safety Population).....	36
Table 14.3.1.2.1: Summary of Treatment-Emergent Adverse Event Characteristics (Safety Population).....	42
Table 14.3.1.2.2: Summary of Treatment-Emergent Adverse Events Leading to Permanent Withdrawal of Study Drug and/or Early Discontinuation From the Study (Safety Population) .....	44
Table 14.3.1.2.3: Summary of Treatment-Emergent Adverse Events by MedDRA System Organ Class and Preferred Term (Safety Population).....	45
Table 14.3.1.2.4: Summary of Treatment-Emergent Adverse Events by Severity (Safety Population).....	46
Table 14.3.1.2.4: Summary of Treatment-Emergent Adverse Events by Relationship (Safety Population).....	47
Table 14.3.2.2.1: Summary of Treatment-Emergent Serious Adverse Event Characteristics (Safety Population).....	48
Table 14.3.2.2.2: Summary of Treatment-Emergent Serious Adverse Events by MedDRA System Organ Class and Preferred Term (Safety Population).....	50
Table 14.3.2.2.3: Summary of Treatment-Emergent Serious Adverse Events by Severity (Safety Population).....	51
Table 14.3.2.2.4: Summary of Treatment-Emergent Serious Adverse Events by Relationship (Safety Population).....	52
Table 14.3.4.1.1: Summary of Hematology Results (Safety Population).....	53
Table 14.3.4.1.2: Summary of Chemistry Results (Safety Population).....	54
Table 14.3.5.1: Summary of Vital Signs by Visit (Safety Population).....	55

Table 14.4.1: Extent of Exposure (Safety Population) .....	59

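### Tolerability is in the primary objective, but local reactions not recorded as AEs are summarised only by visit, so no planned table counts subjects ever affected, their worst grade, or those who worsened

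*SAP*

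**What the plan says.** SAP section 4 gives the primary objective as "to assess the safety and tolerability of KERYDIN (tavaborole) topical solution, 5% applied once daily for 48 weeks in pediatric subjects".

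Section 5.4.3.1 defines six LTR signs, each graded 0 to 3 at Baseline and at every later study visit. They are entered on a dedicated form and, by default, not on the AE form. There is one exception: "LTRs that require treatment (eg, with a concomitant medication or drug interruption or drug discontinuation) are an exception to this guideline". Those reactions are entered on both forms.

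Section 5.5.8.3 states the analysis. The six signs "will be evaluated by frequency tables for Baseline and Weeks 2, 4, 8, 16, 24, 32, 40, 48, and 52", and grade and change from Baseline are also described by mean, SD, median, minimum and maximum. The index in section 6 has two LTR tables, 14.3.1.1.1 (grade frequencies) and 14.3.1.1.2 (means). Both are titled as by-visit summaries, and their shells have visit columns only. The remaining dedicated LTR output is Listing 16.2.7.1 (section 7).

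Adverse events are handled differently. In the causality and severity summaries of section 5.5.8.2, "each subject will be counted only once within an SOC or a preferred term", using the closest relationship and the greatest severity. The footnote to the severity table repeats the rule for severity.

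**The concern.** Two natural descriptive answers to a tolerability objective are how many children had a local reaction during treatment and how severe it became in each of them. By-visit tables show how many subjects were at each grade on each occasion. They do not show whether the subjects affected at Week 8 are the same ones affected at Week 4. A few children with a persistent reaction and many children with one brief reaction can therefore produce the same two tables, although these are different tolerability profiles.

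Keeping LTRs off the AE form also takes them out of the once-per-subject count that they would otherwise get in the TEAE tables, and no other summary replaces it. The route to the AE form depends on action taken, not on grade. A grade 2 or grade 3 reaction that led to no treatment, interruption or discontinuation would stay outside the TEAE tables.

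**Working it through.** The SAP states no LTR rate, no total sample size and no LTR count across visits, so there is no planned figure to reproduce. The check has two parts: what the planned outputs contain, and what they can determine.

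**1. Outputs.**
- Table 14.3.1.1.1: number and percentage at grades 0 to 3, by sign and visit.
- Table 14.3.1.1.2: N, mean, SD, median, minimum and maximum of grade and of change from Baseline, by sign and visit.
- Neither shell has an any-post-baseline row, a worst-grade row, or a count of subjects who worsened.
- Listing 16.2.7.1 holds subject-level data but is not a summary.

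**2. Bounds.** Let c_v be the number of subjects with a given sign at post-baseline visit v. Every affected subject appears in at least one c_v, so

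max(c_v) ≤ subjects ever affected ≤ min(n, Σ c_v).

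The schedule has nine post-baseline LTR visits (Weeks 2, 4, 8, 16, 24, 32, 40, 48 and 52). Treatment lasts 48 weeks (section 5.3), so eight of them run through Week 48. If c_v = k at every visit, the range is k to min(n, 9k), or k to min(n, 8k) through Week 48.

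**3. Illustration.** n = 40 is the minimum number of adolescents in section 5.5.9, used here as an assumed n. The values of k are also assumed.

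| k per visit | nine visits | eight visits through Week 48 | nine visits, if visits were independent: n[1 − (1 − k/n)^9] |
|---|---|---|---|
| 1 (2.5%) | 1 to 9 (2.5% to 22.5%) | 1 to 8 (2.5% to 20%) | 8.2 (20.4%) |
| 2 (5%) | 2 to 18 (5% to 45%) | 2 to 16 (5% to 40%) | 14.8 (37.0%) |
| 4 (10%) | 4 to 36 (10% to 90%) | 4 to 32 (10% to 80%) | 24.5 (61.3%) |

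**4. Identical tables, different answers.** Take n = 40, every Baseline grade 0, and one subject at grade 1 and one at grade 2 at each of the nine visits.
- Each visit shows 38/1/1/0 subjects at grades 0/1/2/3.
- Mean = (1 + 2)/40 = 0.075.
- SD = √[(1 + 4 − 3²/40)/39] = √(4.775/39) = 0.35.
- Median 0, range 0 to 2. With Baseline at 0, the change statistics are the same.

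If each affected subject has the sign at m visits, always at the same grade, then 2 × 9/m subjects are ever affected and half of them have worst grade 2:
- m = 9: 2 ever affected, 1 with worst grade 2.
- m = 3: 6 ever affected, 3 with worst grade 2.
- m = 1: 18 ever affected, 9 with worst grade 2.

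Both planned tables are the same in all three cases. Because Baseline is 0, the number who worsened is also 2, 6 or 18.

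**5. Worsening at one visit.** Suppose 4 of 40 are at grade 1 at Baseline and 4 of 40 at a later visit. Mean change is 0 both when nobody changed (SD 0, range 0 to 0) and when 4 worsened and 4 improved (SD = √(8/39) = 0.45, range −1 to 1). The planned maximum shows that somebody worsened at that visit. Nothing planned gives the number of subjects who worsened over the study.

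**The case against.** The strongest reply is that nothing here is wrong. Section 5.5.8.3, the index, the shells and the listing agree with each other. The study is open-label with a single treatment, no formal power calculation and no inference that rests on these tables, and the missing counts could be derived later from the listing. All of that stands, and it limits the point to an improvement in a descriptive display.

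A reader might infer three stronger things that the SAP does not support.

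- *That troublesome reactions escape per-subject counting.* LTRs needing treatment, interruption or discontinuation go on the AE form and are counted once per subject in the TEAE tables. An untreated grade 3 reaction would still appear in the severe row at its visit, and the highest grade in the study can be read from the by-visit tables.
- *That LTRs alone lack a within-subject summary across visits.* For laboratory values "shift tables will be created according to normal ranges", but the shells compare Baseline with Week 24 and with Week 52 separately and show no worst post-baseline value. Vital signs are also summarised only by visit. The valid contrast is with TEAEs.
- *That 45% or 90% of subjects could plausibly be affected.* Those figures need a different subject affected at every visit and a constant rate at all nine, including Week 52, after the 48-week treatment period. Where a sign appears at one visit only, the two bounds coincide.

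One part of the reply does not hold. The listing is not a substitute for a planned summary: a reader would have to tally six signs over nine visits for each child to answer part of the primary objective.

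**Conclusion.** The point holds as a gap in how part of the primary objective is summarised, for LTRs not also recorded as AEs. The planned tables bound the number of subjects ever affected but do not determine it, and they give neither the distribution of worst grade per subject nor the number who worsened over the study. In the illustration, 2 of 40 affected at each visit is compatible with 2 to 18 subjects over all post-baseline visits, or 2 to 16 through Week 48. The per-visit rates and n = 40 are assumptions, and the upper ends are theoretical bounds, not expected values. That by-visit counts cannot identify the answer when a sign appears at several visits does not depend on those choices. The SAP contains no error or contradiction on this point. The change is worth making because it is cheap and answers the study's own question directly.

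**What to change.** Add to section 5.5.8.3:

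*For each LTR sign and for any LTR, each Safety-population subject with at least one post-baseline LTR assessment will be counted once at the maximum post-baseline grade, with the number of subjects whose maximum exceeds their Baseline grade (for any LTR, subjects in whom at least one sign exceeds its Baseline grade). Results will be shown for visits through Week 48 and for all post-baseline visits including Week 52/ET.*

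Add one matching table to the index in section 6. It should show the number of subjects assessed as the denominator and carry a footnote that LTRs also recorded as AEs appear in the TEAE tables. Keep both by-visit tables as planned.

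The cost is one more descriptive table from data already collected, with no new assessment and no test. Its limitation is that a maximum over visits depends on how many visits a subject attended, so subjects who left early have less opportunity to show a reaction. Showing the number assessed makes the denominator clear but does not remove this dependence.
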